11.2 The Number of Participants

The power calculation is based on the primary outcome of change in appetite hormones and a standard deviation of AUC of 96.2pg/ml of total PYY based on a study looking at the influence of resistance and aerobic exercise on hunger and circulating levels of total PYY in healthy males (Broom 2009). To detect a minimum clinically significant difference of 120pg/ml in AUC of total PYY between groups, we will require 15 participants in each of the four arms with 80% power and 2-sided alpha of 1.7%. This will allow three comparisons between arms. To account for up to 20% dropout, 19 participants will be required in each arm; therefore 76 participants will be recruited in total.

11.3 The Level of Statistical Significance

Statistical significance will be taken at the level of p<0.05.

11.4 Criteria for the Termination of the Trial

No formal criteria for termination of the trial will be set. A Data Safety Monitoring Committee (DSMC) will oversee the trial in terms of safety and efficacy. The DSMC will be made up of two clinicians and a statistician, all of whom will be independent of the trial. The DSMC will assess adverse and serious adverse events unblinded to treatment allocation. The DSMC can make a recommendation to the TSC to stop the trial on both safety and overt efficacy grounds. There are no plans for a formal interim analysis.

11.5 Procedure for Accounting for Missing, Unused, and Spurious Data

Data will be entered into a database with real-time validation, which will limit spurious data. Before analysis begins all data will be checked and any anomalies will be checked against the source data.

During data collection we will attempt to minimise missing data items. Participants with missing data will be excluded on a case-wise basis, i.e. only from those analyses which required the missing items. The primary and main secondary outcomes will be analysed on both a complete case basis and using multiple imputation to estimate the effect of missing data.

11.6 Procedures for Reporting any Deviation(s) from the Original Statistical Plan

A statistical analysis plan will be written and agreed by all investigators prior to database lock. Any deviations from the statistical analysis plan will be stated in the trial publication with the reasons and justification for the deviation.

11.7 Inclusion in Analysis

All analyses of outcome data will be carried out on a complete case basis according to randomised group. Therefore those with missing outcome data will be excluded from this analysis. As a sensitivity analysis, for the primary and main secondary outcome, multiple imputation will be used to perform an intention to treat analysis, and to assess the impact of missing outcome data. We will also conduct a per protocol analysis excluding those who report no longer taking their randomised treatment at the four follow ups.

12. DIRECT ACCESS TO SOURCE DATA/DOCUMENTS

Direct access will be granted to authorised representatives from the Sponsor, host institution and the regulatory authorities to permit trial-related monitoring, audits and inspections.

13. QUALITY CONTROL AND QUALITY ASSURANCE PROCEDURES

The study will be conducted in accordance with the current approved protocol, ICH GCP, relevant regulations and standard operating procedures (SOPs).

Regular monitoring will be performed according to ICH GCP. Data will be evaluated for compliance with the protocol and accuracy in relation to source documents. Following written standard operating procedures, the monitors will verify that the clinical trial is conducted and data are generated, documented and reported in compliance with the protocol, GCP and the applicable regulatory requirements.

As part of the quality management process, a monitoring plan will be developed by the Sponsor in accordance with Sponsor SOPs. The monitoring plan will be based on a study risk assessment which is determined by the level of risk within the study to participant safety, integrity of the trial and trial data validity. All trial monitoring will be conducted in accordance with the monitoring plan and will be undertaken by the trial Sponsor. All monitoring will be performed by staff who are ICH/GCP trained and are competent in monitoring to GCP standards. A documented monitoring log and audit trail will be maintained throughout the lifetime of the study.

The trial manager will also undertake internal audit check to ensure compliance with protocol, GCP and regulatory requirements.

All source data, study documents, and participant notes will be made available for monitoring, audits and inspections by the Ethics Committee, the Sponsor and the Regulatory Authority.

14. CODES OF PRACTICE AND REGULATIONS

14.1 Ethics

Participants will be free to withdraw at any time from the study without giving a reason and without their legal rights being affected. All study procedures including risks involved will be explained clearly to the participant at the Screening Visit and subsequently before each procedure is performed.

The overall care and comfort of the participant will be considered paramount at all times during the study.

14.2 Sponsor Standard Operating Procedures

All relevant Sponsor SOPs will be followed to ensure that this study complies with all relevant legislation and guidelines.

14.3 Declaration of Helsinki

The Investigator will ensure that this study is conducted in full conformity with the current revision of the Declaration of Helsinki (last amended October 2000, with additional footnotes added 2002 and 2004).

14.4 ICH Guidelines for Good Clinical Practice

The Investigator will ensure that this study is conducted in full conformity with relevant regulations and with the ICH Guidelines for Good Clinical Practice (CPMP/ICH/135/95) July 1996.

14.5 Approvals

The trial will not commence until Sponsor green light is given. Once Sponsor (University of Leicester) authorisation has been confirmed, the protocol, informed consent form, participant information sheet and any proposed advertising material will be submitted to an appropriate Research Ethics Committee (REC), regulatory authorities (MHRA in the UK), and host institution's research and development department for written approval.

Once Sponsor authorisation has been confirmed, the Investigator will submit and, where necessary, obtain approval from the above parties for all substantial amendments to the original approved documents.

14.6 Participant Confidentiality

The trial staff will ensure that the participants' anonymity is maintained. The participants will be identified only by initials and a participants ID number on the CRF and any electronic database. All documents will be stored securely and only accessible by study staff and authorised personnel. The study will comply with the Data Protection Act which requires data to be anonymised as soon as it is practical to do so. Samples will only be identified by participant ID number and visit time point.

All research data will be kept in a secure office environment within Leicester Diabetes Centre, Leicester General Hospital during the active phase of the study and until the data have been analysed. It will then be archived in line with University of Leicester policy.

14.7 Other Ethical Considerations

Placebo study drug will be received by 50% of the study participants. The reason for this will be clearly explained to the participant at the screening visit and described in the participant information leaflet.

15. DATA HANDLING AND RECORD KEEPING

The participants will be identified by a study specific participant number and/or code in any database. The name and any other identifying detail will not be included in any study data electronic file.

Each participant will be assigned a unique identification number upon recruitment. Patient contact details will be held on an independent database and used to arrange data collection visits and send out follow-up questionnaires. The database will be password protected and only researchers collecting data will have access. All data collected during the study will be stored anonymously on a separate database on NHS computers. Again access will be password protected and restricted to relevant members of the research team.

Paper copies of the CRFs and questionnaires will be stored in a secure office environment in the Leicester Diabetes Centre, Leicester General Hospital. Neither hard copies nor electronic files containing personal information will be removed from the research office or stored in a non-secure manner electronically. The study research team will comply with the Data Protection Policy of the University of Leicester and the local NHS Trusts.

The Leicester Clinical Trials Unit (CTU) is a UK Clinical Research Collaboration fully registered CTUs and has been involved in this application from the beginning and will be involved throughout the project. The CTU has a well-established IT infrastructure and will be providing support for this study through database development and data management. They will use a Clinical Data Management System called InferMed Macro v4 to set up a tailored data capture method that meets the needs of the study. This is a secure and validated database solution, with quality control mechanisms to ensure that the data collected are complete and accurate. The CTU has a robust quality management system (QMS). All staff working on this project will work within this QMS framework ensuring that the relevant staff are adequately trained, fully supported and working to common standard operating procedures. The CTU will ensure compliance with the appropriate governance, stipulations and trial protocol. The database solutions that the CTU implement using MACRO are designed to meet the requirements of International Conference on Harmonisation GCP and the Medicines for Human Use (Clinical Trials) Regulations 2004. The installation of InferMed Macro and the hosting environment is fully validated is configured using an automatic backup and failover architecture. The hosting agreement sets out a target of 99.95% availability excluding scheduled downtime for maintenance.

All study data will be entered on a customised database developed by the CTU. The electronic data entry system will be validated and SOPs maintained.

16. STUDY GOVERNANCE

The study will be conducted in accordance with the UK Policy Framework for Health and Social Care Research, ICH GCP and the Data Protection Act. The Sponsor responsible for checking research governance arrangements will be the University of Leicester.

16.1 Trial Steering Committee (TSC)

TSC will comprise an independent chair, at least one other independent clinician with expertise in the management of diabetes, the chief investigator and key co-investigators. The trial statisticians may attend as needed. This committee will be responsible for the overall management and oversight of the trial and will meet once prior to start up and then every 6 months, normally within 2 months of the Data Safety Monitoring Committee (DSMC) (although additional meetings may be called by the CI or TSC or DSMC chair) to review and approve protocol amendments and any sub-study proposals, review recruitment rates, protocol adherence, retention, compliance, safety issues, planned analyses and reports and act on recommendations of the DSMC. Minutes from the TSC will be copied to the Sponsor.

16.2 Data Safety Monitoring Committee (DSMC)

The DSMC charter will be prepared as per Sponsor SOP. DSMC will comprise an independent clinician, an independent chair and independent statistician. The chief investigator or trial statistician may be invited to attend to provide specific input by the DSMC Chair. The DSMC will be responsible for the interests and safety of the participants and its main role will be to make advisory recommendations to the TSC. To this end, the DSMC will undertake safety data reviews every six months after recruitment begins, unless otherwise deemed necessary. In addition, the DSMC will review analysis plans.

16.3 Trial Management Group (TMG)

TMG will report to the trial steering committee and will include the chief investigator, other senior investigators and the day-to-day project management team. The group will meet monthly or bi-monthly depending on need, either face-to-face or by teleconference, to discuss the details and logistics of recruitment, retention and follow-up data collection.

17. PUBLICATION POLICY

It is envisaged that the results of the study will be published in the relevant Diabetes Journals and disseminated at national and international conferences and meetings.

Acknowledgement of any supporting organisations, including funders, the University of Leicester, Loughborough University, Leicester Clinical Trials Unit, and Leicester-Loughborough Lifestyle BRU will be included.

APPENDIX 1 – Participant Recruitment Pathway

APPENDIX 2 – Study Questionnaires

SEESAW - Visual Analogue Scale

Visual Analogue Scale

Time: Pre-breakfast (baseline)

Researcher to measure from left to right in mm to give a score between 0-100. Write this score above where participant marks **X**

Place a mark on the horizontal lines below after considering the following questions:

l am not hungry at all	How hungry do you feel?	I have never beer more hungry
I am completely empty	How satisfied do you feel?	l cannot eat another bite
Not at all full	How full do you feel?	Totally full
Nothing at all	How much do you think you can eat?	A lot
Not at all nauseous	How nauseous do you feel?	Very nauseous

SEESAW - Three-Factor Eating Questionnaire

APPENDIX: THREE-FACTOR EATING QUESTIONNAIRE

One point is given for each item in Part I and for each item (numbered question) in Part II. The correct answer for the true/false items is underlined and beside it is the number of the factor that it measures. The direction of the question in Part II is determined by splitting the responses at the middle. If the item is labelled '+', those responses above the middle are given a zero. Vice versa for those with a '-'. For example, anyone scoring 3 or 4 on the first item in Part II (item No. 37) would receive one point. Anyone scoring 1 or 2 would receive a zero.

Part I

				Factor Number
1.	When I smell a sizzling steak or see a juicy piece of meat, I find it very difficult to keep from eating, even if I have just finished a meal.	т	F	2
2.	I usually eat too much at social occasions, like parties and picnics.	$\frac{T}{T}$	F	2
3.	I am usually so hungry that I eat more than three times a day.	÷	F	3
4.	When I have eaten my quota of calories, I am usually good about not eating	-	•	
4.	any more.	Ť	F	1
5.	Dieting is so hard for me because I just get too hungry.	Ŧ	F	3
6.	I deliberately take small helpings as a means of controlling my weight.	T	F	1
7.	Sometimes things just taste so good that I keep on eating even when I am no longer hungry.	т	F	2
8.	Since I am often hungry, I sometimes wish that while I am eating, an expert would tell me that I have had enough or that I can have something more	-		
	to eat.	T	F	3
9.	When I feel anxious, I find myself eating.	T T	F	2
10.	Life is too short to worry about dieting.	T	F	1
11.	Since my weight goes up and down, I have gone on reducing diets more than once.	Т	F	2
12.	I often feel so hungry that I just have to eat something.	T	F	3
13.	When I am with someone who is overeating, I usually overeat too.	T	F	2
14.	I have a pretty good idea of the number of calories in common food.	T T T T	F	1
15.	Sometimes when I start eating, I just can't seem to stop.	T	F	2
16.	It is not difficult for me to leave something on my plate.	T	F	2
17.	At certain times of the day, I get hungry because I have gotten used to eating then.	т	F	3
18.	While on a diet, if I eat food that is not allowed, I consciously eat less for a	-	•	-
10.	period of time to make up for it.	T	F	1
19.	Being with someone who is eating often makes me hungry enough to eat also.	T	F	3
20.	When I feel blue, I often overeat.	T	F	2
21.	I enjoy eating too much to spoil it by counting calories or watching my weight.	T	F	1
22.	When I see a real delicacy, I often get so hungry that I have to cat right away.	T	F	3
23.	I often stop eating when I am not really full as a conscious means of limiting the amount that I eat.	T	F	1
24.	I get so hungry that my stomach often seems like a bottomless pit.	Ť.	F	3
25.	My weight has hardly changed at all in the last ten years.	Ť	F	2
26.	I am always hungry so it is hard for me to stop eating before I finish the	•	-	-
	food on my plate.	T	F	3
27.	When I feel lonely, I console myself by eating.	T	F	2
28.	I consciously hold back at meals in order not to gain weight.	$\frac{T}{T}$	F	1
29.	I sometimes get very hungry late in the evening or at night.	T	F	3

30.	I eat anything I want, any time I want.	T	F	1
31.	Without even thinking about it, I take a long time to eat.	T	F	2
32.	I count calories as a conscious means of controlling my weight.	T	F	1
33.	I do not eat some foods because they make me fat.	T	F	1
34.	I am always hungry enough to cat at any time.	T	F	3
35.	I pay a great deal of attention to changes in my figure.	T	F	1
36.	While on a diet, if I eat a food that is not allowed, I often then splurge and	_		
	eat other high calorie foods.	T	F	2

Part II

Directions: Please answer the following questions by circling the number above the response that is appropriate to you.

37.	How often are you die	ting in a conscious effo	ort to control your weig	ht?		
	1	2	1	4		
	rarely	sometimes	usually	always	+	1
38.	Would a weight fluctu	ation of 5 lbs affect the	e way you live your life	?		
	1	2	3	4		
	not at all	slightly	moderately	very much	+	1
39.	How often do you fee	l hungry?				
	1	2	3	4		
	only at	sometimes	often between	almost		
	mealtimes	between meals	meals	always	+	3
40.	Do your feelings of gu	ilt about overeating he	lp you to control your !	food intake?		
	1	2	3	4		
	never	rarely	often	always	+	ŀ
41.	How difficult would i next four hours?	t be for you to stop eat	ing halfway through di	inner and not eat for the		
	1	2	3	4		
	easy	slightly	moderately	very		
		difficult	difficult	difficult	+	3
42.	How conscious are yo	u of what you are eatin	g?			
	1	2	3	4		
	not at all	slightly	moderately	extremely	+	1
43.	How frequently do yo	u avoid 'stocking up' o	on tempting foods?			
	1	2	3	4		
	almost never	seldom	usually	almost always	+	١
44.	How likely are you to	shop for low calorie fo	ods?			
	1	2	3	4		
	unlikely	slightly unlikely	moderately likely	very likely	+	1
45.	Do you eat sensibly in	front of others and sp	lurge alone?			
	1	ż	3	4		
	never	rarely	often	always	+	2
46.	How likely are you to	consciously eat slowly	in order to cut down or	n how much you eat?		
	1	2	3	4		
	unlikely	slightly likely	moderately likely	very likely	+	1

47.	How frequently do y	ou skip dessert becau	ise you are no longer nung	ry?		
	1	2	3	4		
	almost never	seldom	at least once a week	almost every day	- 3	
48.	How likely are you to	o consciously eat less	than you want?			
	1	2	3	4		
	unlikely	slightly likely	moderately likely	very likely	+ 1	
49.	Do you go on cating	binges though you ar	e not hungry?			
	1	2	3	4		
	never	rarely	sometimes	at least once a week	+ 2	
50.		ns total restraint (co	estraint in eating (eating v nstantly limiting food int			
		0				
	eat whatever you wa	ınt, whenever you wa	nt it		+ 1	
		1				
	usually eat whatever	you want, whenever	you want it			
		2				
	often eat whatever	you want, whenever	you want it			
	often limit food inte	3 ike, but often 'give in				
	orten mint 1000 mta	ike, bat often give in				
		4				
	usually limit food intake, rarely 'give in'					
		5				
	constantly limiting f	ood intake, never 'gi	ving in'			
51.	but because of any r	number of things that	ribe your eating behavior happen during the day, be eting again tomorrow.'			
	1	2	3	4		
	not like me	little like me	pretty good description of me	describes me perfectly	+ 2	

SEESAW – International Physical Activity Questionnaire (IPAQ)

INTERNATIONAL PHYSICAL ACTIVITY QUESTIONNAIRE

Name	Sex (F/M)	Ageyrs	
We are interested in finding out about the kinds as part of their everyday lives.	of physical act	ivities that people do	0
The questions will ask you about the time you s 7 days.	pent being phy	sically active in the I	ast
Please answer each question even if you do no person.	ot consider your	rself to be an active	
To describe the intensity of the physical activity are used:	, two terms (Mo	oderate and Vigorous	s)
Moderate activities refer to activities that take n	noderate physic	cal effort and make	
you breathe somewhat harder than normal.			
Vigorous physical activities refer to activities the you breathe much harder than normal.	at take hard ph	ysical effort and mak	e

Thank you for participating!

time spent at work, at home, while doing course work and during leisure time. This may include time spent sitting at a desk, visiting friends, reading, or sitting or lying down to watch television. During the last 7 days, how much time did you spend sitting during a day? hours ___ minutes 2 Think about the time you spent walking in the last 7 days. This includes at work and at home, walking to travel from place to place, and any other walking that you might do solely for recreation, sport, exercise, or leisure. During the last 7 days, on how many days did you walk for at least 10 minutes at a ⇒ How much time did you usually spend walking on _ Days one of those days? or __ hours ___ minutes □ No day 3. During the last 7 days, on how many days did you do moderate physical activities like gardening, cleaning, bicycling at a regular pace, swimming or other fitness Think only about those physical activities that you did for at least 10 minutes at a time. Do not include walking. ⇒ How much time did you usually spend doing ___ Days moderate physical activities on one of those days? □ No day ___ hours ___ minutes 4. During the last 7 days, on how many days did you do vigorous physical activities like heavy lifting, heavier garden or construction work, chopping woods, aerobics, jogging/running or fast bicycling? Think only about those physical activities that you did for at least 10 minutes at a time. How much time did you usually spend doing ___ Days vigorous physical activities on one of those days? □ No day ___ hours ___ minutes

The first question is about the time you spent sitting during the last 7 days. Include

IPAQ-E (English version)

INTERNATIONAL PHYSICAL ACTIVITY QUESTIONNAIRE (August 2002)

SHORT LAST 7 DAYS SELF-ADMINISTERED FORMAT

FOR USE WITH YOUNG AND MIDDLE-AGED ADULTS (15-69 years)

The International Physical Activity Questionnaires (IPAQ) comprises a set of 4 questionnaires. Long (5 activity domains asked independently) and short (4 genericitems) versions for use by either telephone or self-administered methods are available. The purpose of the questionnaires is to provide common instruments that can be used to obtain internationally comparable data on health—related physical activity.

Background on IPAQ

The development of an international measure for physical activity commenced in Geneva in 1998 and was followed by extensive reliability and validity testing undertaken across 12 countries (14 sites) during 2000. The final results suggest that these measures have acceptable measurement properties for use in many settings and in different languages, and are suitable for national population-based prevalence studies of participation in physical activity.

Using IPAQ

Use of the IPAQ instruments for monitoring and research purposes is encouraged. It is recommended that no changes be made to the order or wording of the questions as this will affect the psychometric properties of the instruments.

Translation from English and Cultural Adaptation

Translation from English is supported to facilitate worldwide use of IPAQ. Information on the availability of IPAQ in different languages can be obtained at www.ipaq.ki.se. If a new translation is undertaken we highly recommend using the prescribed back translation methods available on the IPAQ website. If possible please consider making your translated version of IPAQ available to others by contributing it to the IPAQ website. Further details on translation and cultural adaptation can be downloaded from the website.

Further Developments of IPAQ

International collaboration on IPAQ is on-going and an *International Physical Activity Prevalence Study* is in progress. For further information see the IPAQ website.

More Information

More detailed information on the IPAQ process and the research methods used in the development of IPAQ instruments is available at www.ipaq.ki.se and Booth, M.L. (2000).

Assessment of Physical Activity: An International Perspective. Research Quarterly for Exercise and Sport, 71 (2): s114-20. Other scientific publications and presentations on the use of IPAQ are summarized on the website.

SHORT LAST 7 DAYS SELF-ADMINISTERED version of the IPAQ. Revised August 2002

INTERNATIONAL PHYSICAL ACTIVITY QUESTIONNAIRE

We are interested in finding out about the kinds of physical activities that people do as part of their everyday lives. The questions will ask you about the time you spent being physically active in the last 7 days. Please answer each question even if you do not consider yourself to be an active person. Please think about the activities you do at work, as part of your house and yard work, to get from place to place, and in your spare time for recreation, exercise or sport.

Think about all the **vigorous** activities that you did in the **last 7 days**. **Vigorous** physical activities refer to activities that take hard physical effort and make you breathe much harder than normal. Think *only* about those physical activities that you did for at least 10 minutes at a time.

1.	activities like heavy lifting, digging, aerobics, or fast bicycling?
	days per week
	No vigorous physical activities Skip to question 3
2.	How much time did you usually spend doing ${\bf vigorous}$ physical activities on one of those days?
	hours per day
	minutes per day
	Don't know/Not sure
activiti some	about all the moderate activities that you did in the last 7 days . Moderate ies refer to activities that take moderate physical effort and make you breathe what harder than normal. Think only about those physical activities that you did least 10 minutes at a time.
3.	During the last 7 days , on how many days did you do moderate physical activities like carrying light loads, bicycling at a regular pace, or doubles tennis? Do not include walking.
	days per week
	No moderate physical activities Skip to question 5

SHORT LAST 7 DAYS SELF-ADMINISTERED version of the IPAQ. Revised August 2002.

4.	How much time did you usually spend doing moderate physical activities on one of those days?
	hours per day
	minutes per day
	Don't know/Not sure
home	about the time you spent walking in the last 7 days . This includes at work and at , walking to travel from place to place, and any other walking that you have done for recreation, sport, exercise, or leisure.
5.	During the last 7 days , on how many days did you walk for at least 10 minutes at a time?
	days per week
	No walking → Skip to question 7
6.	How much time did you usually spend walking on one of those days?
	hours per day
	minutes per day
	Don't know/Not sure
days. time.	ist question is about the time you spent sitting on weekdays during the last 7 Include time spent at work, at home, while doing course work and during leisure This may include time spent sitting at a desk, visiting friends, reading, or sitting or lown to watch television.
7.	During the last 7 days, how much time did you spend sitting on a week day?
	hours per day
	minutes per day
	Don't know/Not sure
This	is the end of the questionnaire, thank you for participating.
SHORT	LAST 7 DAYS SELF-ADMINISTERED version of the IPAQ. Revised August 2002.

Page 64 of 64

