5.2 Secondary outcome definitions

Below is a list of all of the secondary outcomes collected at baseline and at least one followup visit. Outcomes measured at 2, 6 and 12 weeks will be treated as secondary outcomes.

(i) Appetite hormones ghrelin and GLP-1 and appetite perception Ghrelin and GLP-1 will each be recorded in the same manner as the primary outcome, i.e. as time averaged AUC.

(ii) Resting energy expenditure

(iii) Change in blood and urine biochemical parameters.

- Insulin time averaged AUC
- Glucose time averaged AUC
- Glucagon time averaged AUC
- C-peptide time averaged AUC

The above biochemical parameters will be measured at 7 time points specifically, fasted (pre-standardised breakfast), 30 minutes post-breakfast and then 60 minutes, 90

minutes, 120 minutes, 150 minutes and 180 minutes post-breakfast. Time averaged AUC values will be calculated as per that for PYY.

- Leptin
- HbA1c
- C-reactive protein
- Fasting plasma glucose
- Lipids (total HDL and LDL cholesterol, FFAs)
- eGFR
- urinary glucose excretion
- ALT
- Leptin

(iv) Physical activity measures:

 ActiGraph for assessment of daily step count and daily time spent sedentary and in light-intensity and moderate-to-vigorous intensity physical activity (including only those people with at least 3 days of data)

(v) Study questionnaires

- Three-Factor Eating Questionnaire this will assess the patient's eating traits (restraint, disinhibition, hunger)
- International Physical Activity Questionnaire (IPAQ) —to assess walking, moderate and vigorous activities, along with time spent sedentary.
- Visual Analogue Scale (VAS) which will measure perceived hunger, fullness, satisfaction and prospective food consumption ratings. VAS is measured at every time point as per the blood samples and so will also be analysed as an AUC measure, as per that for PYY.

(vi) Anthropometric measures:

- Body weight (kg)
- Body fat (%)
- Fat mass (kg)
- Bone mass (kg) and density (g/m²)
- Muscle mass (kg)
- Waist circumference (cm)
- Hip circumference (cm)

(vii) Cardiovascular measures:

- Blood pressure (mmHg)
- Resting heart rate (bpm)

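### The Part II scoring sentence for the Three-Factor Eating Questionnaire contradicts its own worked example, and the SAP gives no key to settle which applies

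*Protocol*

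**What the plan says.** Protocol Appendix 2 reproduces the questionnaire with its scoring instructions.

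- **Part I (items 1 to 36)** has its own key: "The correct answer for the true/false items is underlined and beside it is the number of the factor that it measures".
- **Part II (items 37 to 51)** is scored by splitting the responses at the middle. For items marked plus, "those responses above the middle are given a zero". Minus items are covered by a short clause, "Vice versa for those with a" minus sign.
- **The worked example** comes next: "anyone scoring 3 or 4 on the first item in Part II (item No. 37) would receive one point". It then gives the other half: "Anyone scoring 1 or 2 would receive a zero".
- **Item 37's own entry** ends "rarely sometimes usually always + 1", that is, marked plus and assigned to factor 1 (restraint).
- **Item 47** is the only minus item. Its entry ends "almost every day - 3", so it belongs to factor 3 (hunger).

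SAP section 5.2 (v) lists the questionnaire among the secondary outcomes, as a measure of "eating traits (restraint, disinhibition, hunger"). SAP section 5.3.3 analyses all other secondary outcomes by the approach used for the primary outcome. Neither section gives a scoring rule.

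**The concern.** For a response of 3 or 4 on item 37, the general sentence gives 0 and the example gives 1. The instructions therefore give two opposite directions for Part II, and these are the only scoring instructions in the two documents.

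What is at stake is the meaning of three secondary outcomes that bear on the appetite question. Part I has a separate key, so an error in Part II would not simply flip a scale. It would set one part of the scale against the other, and a treatment effect would partly cancel within the score. Restraint has the most Part II items. It is also the trait closest to the energy restriction diet, which features in two of the three comparisons with placebo (SAP section 2.4). A range check would not reveal the error, because the mis-scored totals stay within the normal range.

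**Working it through.** **Step 1. Rule against example.** Item 37 is marked plus.

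| Response to item 37 | General sentence | Worked example |
|---|---|---|
| 3 or 4 (above the middle) | 0 | 1 |
| 1 or 2 (below the middle) | 1 | 0 |

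The sentence does not reproduce the document's own example.

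**Step 2. Which direction fits the items.** Under the sentence, a person who always diets to control weight (item 37) scores zero on restraint, and a person who almost always feels hungry (item 39) scores zero on hunger. Item 47 is an independent check because its sign is minus. The sentence would award a hunger point for skipping dessert almost every day because hunger has gone. The example's direction makes all three items coherent.

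**Step 3. How many items are affected.** Part II has 15 items, 14 plus and one minus. The reversal clause flips item 47 as well, so the two directions disagree on 15 of 15.

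**Step 4. Items per scale**, counted from the factor numbers in Appendix 2:

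| Scale | Part I (*a*) | Part II (*b*) | Total |
|---|---|---|---|
| Restraint (factor 1) | 12 | 9 (items 37, 38, 40, 42, 43, 44, 46, 48, 50) | 21 |
| Disinhibition (factor 2) | 13 | 3 (items 45, 49, 51) | 16 |
| Hunger (factor 3) | 11 | 3 (items 39, 41, 47) | 14 |
| All | 36 | 15 | 51 |

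**Step 5. Maximum contrast.** Take a person who gives every keyed answer and a person who gives none.

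- By the example they score *a* + *b* and 0, a contrast of *a* + *b*.
- By the sentence they score *a* and *b*, a contrast of *a* − *b*.
- The fraction left is (*a* − *b*)/(*a* + *b*). If every item shifts equally, the same fraction applies to a mean treatment difference in points.

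| Scale | By the example | By the sentence | Fraction left |
|---|---|---|---|
| Restraint | 21 | 12 − 9 = 3 | 3/21 = 14% |
| Disinhibition | 16 | 13 − 3 = 10 | 10/16 = 63% |
| Hunger | 14 | 11 − 3 = 8 | 8/14 = 57% |

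**Step 6. Sensitivity to two labels.** The factor numbers of items 40 and 43 are not legible in the extracted text and were read as 1. This is a reading problem, not a fault of the plan. If neither item belonged to restraint, that scale would have 12 + 7 = 19 items. The contrast would fall from 19 to 12 − 7 = 5, leaving 5/19 = 26%. The disinhibition and hunger rows also take items 40 and 43 as restraint items.

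**Step 7. Standardised effect.** The contrast ignores the change in spread, so a one-factor simulation was run. It used binary items with a common loading of 0.3, 0.5 or 0.7 and a trait shift of 0.5 SD. These values are assumptions, not figures from the documents.

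| Scale | Standardised effect by the example (loading 0.3 / 0.5 / 0.7) | By the sentence |
|---|---|---|
| Restraint | 0.37 / 0.44 / 0.45 | 0.08 / 0.13 / 0.20 |
| Disinhibition | 0.35 / 0.43 / 0.45 | 0.27 / 0.37 / 0.42 |
| Hunger | 0.34 / 0.42 / 0.45 | 0.23 / 0.34 / 0.40 |

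The correlation between the two versions of the restraint score was 0.21, 0.31 and 0.44. The ordering agrees with Step 5: restraint is badly damaged and the other two scales much less so.

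**The case against.** The strongest reply is that the appendix largely corrects itself. The example stands next to the faulty sentence and gives the direction twice, for high and for low responses. The item wording and the single minus sign agree with it. A scorer would have to pass over all of this to score Part II backwards. The faulty sentence also sits in the key of an appended questionnaire that Protocol section 8.5 calls validated, not in the statistical sections. Protocol section 5.3 declares the secondary endpoints exploratory.

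Most of this stands, and it limits the point. A reader might infer that the questionnaire results are, or will be, wrongly scored. The documents do not support that: they do not show the scoring code, and the harm arises only if the sentence rather than the example is programmed. A reader might also infer that all three scales lose their meaning. The arithmetic does not support that either, since only restraint comes close to cancelling.

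What the reply does not remove is the contradiction itself. A programmer who codes the general rule and does not test it on item 37 has followed a written instruction, and the SAP contains nothing to stop this.

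**Conclusion.** The point holds as an internal contradiction in a scoring instruction for SAP secondary outcomes. That the two statements conflict is certain. That the example is the intended direction is well supported by the items.

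The percentages in the working are a conditional worst case. They require that the sentence is coded and applied to all of Part II, that Part I is scored correctly, and that items carry equal effects. The restraint figure is 14% on the likely reading of items 40 and 43 and 26% if neither is a restraint item; it should not be quoted without that range. Nothing here touches the PYY outcome, the sample size or the control of multiplicity for the primary comparisons. It should still be corrected before analysis, because the error would be hard to see in the results and is very cheap to exclude.

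**What to change.** 1. In Protocol Appendix 2, correct the general sentence so that plus items score 1 for responses above the middle and 0 below it, and minus items score the reverse. This agrees with the worked example.
2. State that key in SAP section 5.2 (v), with the items that form each scale. Include the split for item 50, which has six responses numbered 0 to 5, so the middle lies between 2 and 3. Confirm the factor of items 40 and 43 from the legible page.
3. Before analysis, test the scoring code on item 37 (3 or 4 gives 1; 1 or 2 gives 0) and on item 47 (the two higher responses give 0; the two lower give 1).

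The cost is one corrected sentence, a short addition to the SAP and a brief code check. If item-level responses are stored, any rescoring needs no new data.
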